APPENDIX M3 – DETAILED CIMA-Q PROJECT PROTOCOL

ABBREVIATIONS

A β : Bêta-Amyloïde

AD: Alzheimer's Disease

ADL: Activities of Daily Living

ADCS-PI: Alzheimer's disease cooperative study – Prevention Instrument

AI: Apathy Inventory

ALP: Alkaline Phosphatase

AST: Alanine Transaminase

BDNF: Brain-Derived Neurotrophic Factor

bFGF: Basic Fibroblast Growth Factor

BORB: Birmingham Object Recognition Battery

BUN: Blood Urea Nitrogen

CCI: Cognitive Change Index

CCNA: Canadian Consortium on Neurogeneration in Aging

CDR: Clinical Dementia Rating

CERAD: Consortium to Establish a Registry for Alzheimer's Disease

CH: Cognitively Healthy

CHUQ: Centre Hospitalier Universitaire de Québec

CIHR: Canadian Institutes of Health Research

CIMA-Q: Consortium for the Early Identification of Alzheimer's Disease - Québec

CPT: Cell Preparation Tube

CRIUGM: Centre de Recherche de l'Institut Universitaire de Gériatrie de Montréal (IUGM Research center)

CRP: C-Reactive Protein

CSF: Cerebrospinal Fluid

DNA: Deoxyribonucleic Acid

DSM-IV: Diagnostic and Statistical Manual of Mental Disorders, version IV

EDTA: Ethylene Diamine Tetraacetic Acid

eMCI: early Mild Cognitive Impairment

FDG: Fluorodeoxyglucose.

FLT: Fms-like Tyrosine Kinase

FRQS: Fonds de Recherche en Santé - Québec

GAI: Geriatric Anxiety Inventory

GDS-30: Geriatric Depression Scale

HbA1c: Glycated Hemoglobin

ICAM: InterCellular Adhesion Molecule

ICAO: International Civil Aviation Organization

IFN: Interferon

IL: Interleukine

INR: International Normalized Ratio

IP: Interferon gamma-induced Protein

ISI: Insomnia Severity Index

IUGM: Institut Universitaire de Gériatrie de Montréal

IUSMQ: Institut Universtaire en Santé Mentale de Québec

IMCI: late Mild Cognitive Impairment

LP: Lumbar Puncture

MCI: Mild Cognitive Impairment

MCI-AD: Mild cognitive impairment – Alzheimer disease

MCP: Monocyte Chemoattractant Protein

MDC: Macrophage-Derived Chemokine

MIP: Macrophage Inflammatory protein

ML: Millilitre

MNA® SF: Mini Nutritional Assessment Short form

MoCA: Montreal Cognitive Assessment

MRI: Magnetic Resonance Imaging

MRS: Magnetic Resonance Spectroscopy

MSSS: Ministère de la Santé et des Services Sociaux

mSv: Millisievert

NIA-AA: National Institute of Aging – Alzheimer’s Association

NPI-Q: Neuropsychiatric Inventory

PET: Positron Emission Tomography

PHQ-9: Patient Health Questionnaire

PLGF: Placenta Growth Factor

1. INTRODUCTION

People 65 years of age and older currently account for 16% of the population in Quebec; they are now more numerous than individuals under the age of 15. This spectacular transformation of the demographic landscape is a demanding challenge and calls for significant research efforts in order to reduce the considerable impact of age-related diseases on autonomy and quality of life among this significant segment of the population. Alzheimer's disease (AD) is a condition that should be prioritized. Indeed, in addition to being devastating and incurable, it is also the most common neurological disease among elderly people. AD and related diseases affect 10% of individuals after the age of 65 and this percentage increases to 35% after the age of 85. Coordinated efforts are necessary to reduce the psychological, social and economic burden that the disease places on patients, their families and society as a whole. Two principal challenges of this project are: **(1)** To develop new methods enabling earlier diagnosis. Presently speaking, AD is diagnosed at the dementia stage, once the symptoms have had a considerable impact on quality of life and autonomy and the brain has sustained serious damage. **(2)** To acquire a better understanding of the etiology of AD in order to develop more effective treatments.

2. STUDY OBJECTIVES

The specific objectives are:

- (1)** Identify sensitive and specific tests for diagnosing AD early at prodromal (MCI) and preclinical (SCI) stages;
- (2)** Develop new neuroimaging markers;
- (3)** Identify new biological and genetic markers;
- (4)** Develop an effective “toolbox” combining cognitive, neuroimaging and biomarker data;
- (5)** Identify early molecular mechanisms contributing to evolution towards MCI, SCI, and AD stages;
- (6)** Identify lifestyles that predispose one to developing the disease and preventative factors;
- (7)** Implement structured clinical procedures for diagnosing and biomarker analyses in memory clinics.

3. RESEARCH PLAN

3.1 LONGITUDINAL STUDY PLAN

*See full assessment and interim visit details in Table 1.

3.2 TARGET POPULATION

The principal aim of this project is to recruit participants who are representative of the different Alzheimer's disease stages (pre-symptomatic and symptomatic) and clinical situations (comorbidity, etc.). Moreover, we invite cognitively healthy elderly volunteers and healthy young volunteers to participate in order to obtain comparison values (targeted cognitive and biological measures). The participants will be recruited from the following settings: (1) the NuAge cohort, (2) participating memory clinics (3) the community (advertisements and participant banks at participating sites) and (4) the CCNA project.

3.3 SAMPLE SIZE

3.3.1 Participants 65 years of age and older

In this study, approximately 350 elderly participants (65 years and older) will be recruited to form groups comprised of the following proportions:

- I. 50 participants classified as CH (Cognitively Healthy)
- II. 150 participants classified as SCD (Subjective Cognitive Decline)
- III. 100 participants classified as MCI (Mild Cognitive Impairment), early or late
- IV. 50 participants classified as mild AD (Alzheimer's Dementia)

In order to obtain 350 study admissible participants, we plan to screen approximately 650 potential participants. All participants included in the study (350) will be assessed in neuropsychology and neuropsychiatry, and will provide blood samples and undergo a basic clinical assessment (clinical questionnaires, neurological and physical examination, blood tests). Imaging assessments (MRI) will be conducted (62) among the greatest number of participants possible (approximately 16.7% of CH, 50% of SCI, 16.7% of MCI, 16.7% of AD). Our objective is to collect cerebrospinal fluid (CSF) from 80 participants (approximately 20 per Dx group) for analysis of known biomarkers such as A β 1-42, Tau and phospho-Tau, or future biomarkers associated with aging (59, 60, 61). We plan on conducting FDG-PET among around 35 participants according to the following approximate proportions: 20 SCI, 12 MCI and 3 mild AD. Finally, for those who consent, their brain will be collected upon death and sent to the Brain Bank, in compliance with Brain Bank procedures and rules.

3.3.2 Participants 20 to 45 years of age

In addition to the targeted cohort of 350 elderly people 65 years and older, we plan on recruiting 20 young participants (20-45 years old) who will act as controls for biomarker analyses (YCH). We plan on using CSF samples of young patients for whom a CSF sample (10 to 15 mL) has already been collected within the scope of usual care (for example, to rule out a clinical diagnosis). The unused portion of these samples is usually destroyed, and it is this unused portion we plan to use. This strategy will be put into place at the CHU de Quebec-Université Laval. To do so, a member of the CHU de Quebec-Université Laval clinical team will contact patients aged 20 to 45 years who have already undergone a lumbar puncture to inform them of the CIMA-Q project and to obtain their permission to forward their name and contact information to the CIMA-Q team. Consenting patients will be contacted by a CIMA-Q team member. These potential participants will answer a screening questionnaire to determine their eligibility. This form is similar to the screening questionnaire for elderly patients. Once the patient's eligibility is confirmed, a consent form will be sent to the potential participant who must then sign and return it by email or mail, in order to obtain their permission to use the unused CSF for the CIMA-Q project. Once the signed form received, the CIMA-Q research team can ask for the CSF sample to be transferred.

These samples will be preserved according to the procedures described in this protocol for CSF samples at the Quebec BioBank site.

3.4 INCLUSION CRITERIA FOR THE COGNITIVELY HEALTHY (CH) OR NORMAL ELDERLY GROUP

3.4.1 Answers (a) or (b) to this question about cognitive complaints (1)

“Do you think that your memory is getting worse?”

- a. No
- b. Yes, but I'm not worried about it
- c. Yes, and it worries me

3.4.2 Has a deferred recall score on Logical memory (Wechsler Memory Scale, max score of 25) (2)

- I. ≥ 9 for 16 years of education and more
- II. ≥ 5 for 8-15 years of education
- III. ≥ 3 for 0-7 years of education.

3.4.3 Has a score of 26 or more ($\geq 26/30$) on the Montreal Cognitive Assessment (MoCA) (3).

3.4.4 Has a CDR (Clinical Dementia Rating) (4, 5) score of 0.

3.5 INCLUSION CRITERIA FOR THE SUBJECTIVE COGNITIVE IMPAIRMENT (SCI) GROUP

3.5.1 Answers (c) to this question about cognitive complaints

“Do you think that your memory is getting worse?”

- a. No
- b. Yes, but I'm not worried about it
- c. Yes, and it worries me

3.5.2 Has a deferred recall score on Logical memory (Wechsler Memory Scale, max score of 25)

- I. ≥ 9 for 16 years of education and more
- II. ≥ 5 for 8-15 years of education
- III. ≥ 3 for 0-7 years of education

3.5.3 Has a score of 26 or more ($\geq 26/30$) on the (MoCA)

3.5.4 Has a CDR (Clinical Dementia Rating) score of 0.

3.6 INCLUSION CRITERIA FOR THE EARLY MILD COGNITIVE IMPAIRMENT (eMCI) GROUP

3.6.1 Answers (b) or (c) to this question about cognitive complaints

“Do you think that your memory is getting worse?”

- a. No
- b. Yes, but I’m not worried about it***
- c. Yes, and it worries me

*** Certain participants are not worried, but the informant is.

3.6.2 Has a deferred recall score on Logical memory (Wechsler Memory Scale, max score of 25)

- I. 9-11 for 16 years of education and more
- II. 5-9 for 8-15 years of education
- III. 3-6 for 0-7 years of education

3.6.3 Has a score of 20 to 26 (inclusively) on the MoCA

3.6.4 Has a CDR (Clinical Dementia Rating) score of 0.5

3.6.5 Meets NIA-AA clinical criteria for MCI-AD (6)

3.7 INCLUSION CRITERIA FOR THE LATE MILD COGNITIVE IMPAIRMENT (IMCI) GROUP

3.7.1 Answers (b) or (c) to this question about cognitive complaints

“Do you think that your memory is getting worse?”

- a. No
- b. Yes, but I’m not worried about it***
- c. Yes, and it worries me

*** Certain participants are not worried, but the informant is.

3.7.2 Has a deferred recall score on Logical memory (Wechsler Memory Scale, max score of 25)

- I. ≤ 8 for 16 years of education and more
- II. ≤ 4 for 8-15 years of education
- III. ≤ 2 for 0-7 years of education.

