3.7.3 Has a score of 20 to 25 (inclusively) on the MoCA

3.7.4 Has a CDR (Clinical Dementia Rating) score of 0.5

3.7.5 Meets NIA-AA clinical criteria for MCI-AD

3.8 INCLUSION CRITERIA FOR MILD AD (ALZHEIMER’S DISEASE) PATIENTS

3.8.1 Has a deferred recall score for the logical story (Wechsler Memory Scale, max score of 25)

- I. ≤ 8 for 16 years of education and more
- II. ≤ 4 for 8-15 years of education
- III. ≤ 2 for 0-7 years of education.

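### Early MCI accepts a MoCA of 26 and late MCI stops at 25, so at MoCA 26 and CDR 0.5 a participant with worse delayed recall fits no group

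*Protocol*

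**What the plan says.** All places are in the Protocol.

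- **Early MCI (3.6):** complaint answer (b) or (c); delayed recall 9-11, 5-9 or 3-6 for 16 or more, 8-15 or 0-7 years of education; MoCA "Has a score of 20 to 26 (inclusively) on the MoCA"; CDR 0.5; NIA-AA criteria for MCI-AD.
- **Late MCI (3.7):** the same complaint answers, CDR and NIA-AA requirement; delayed recall at most 8, 4 or 2 in the same education bands; MoCA "Has a score of 20 to 25 (inclusively) on the MoCA".
- **Cognitively healthy (3.4) and SCI (3.5):** MoCA "Has a score of 26 or more" in both groups, CDR 0 ("3.4.4 Has a CDR (Clinical Dementia Rating) (4, 5) score of 0" and "3.5.4 Has a CDR (Clinical Dementia Rating) score of 0"), and delayed recall of at least 9, 5 or 3.
- **Mild AD (3.8):** the late-MCI recall limits, MoCA 13 to 24, CDR 1.0.

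Section 3.3.1 sets one target of 100 for MCI, early and late together. The protocol explains neither the one-point difference between the MCI ceilings nor what happens to someone who fits no group.

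**The concern.** Complaint, CDR and NIA-AA requirement are identical in the two MCI strata, so delayed recall is what should separate them. A second, unexplained difference in the MoCA ceiling has two effects.

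First, eligibility runs against severity at one score. Of two people alike in everything but recall, both with MoCA 26, the one with the better memory is enrolled and the one with the worse memory is not.

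Second, MoCA is cut off at different points in the two strata. Part of any early-late difference on MoCA, or on measures correlated with it, then comes from the entry criteria.

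Diagnostic group matters elsewhere in the plan: it sets the recruitment targets and the aim of about 20 CSF samples per group (3.3.1), and withdrawn participants are replaced from the same group (3.14).

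**Working it through.** There is no figure of the plan's own to reproduce. The check has two parts.

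**1. Applying the criteria.** Every combination of complaint answer (3), education band (3), delayed recall 0-25 (26 values), MoCA 0-30 (31 values) and CDR 0, 0.5 or 1 (3) was classified by sections 3.4 to 3.8, with the NIA-AA criteria taken as met. That is 3 × 3 × 26 × 31 × 3 = 21,762 profiles. Of these, 1,899 fit exactly one group, 19,863 fit none, and none fits two.

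For CDR 0.5 and complaint (b) or (c):

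| Education (years) | Recall | MoCA 25 | MoCA 26 | MoCA 27 |
|---|---|---|---|---|
| 16 or more | 9-11 | early MCI | early MCI | none |
| 16 or more | 0-8 | late MCI | **none** | none |
| 8-15 | 5-9 | early MCI | early MCI | none |
| 8-15 | 0-4 | late MCI | **none** | none |
| 0-7 | 3-6 | early MCI | early MCI | none |
| 0-7 | 0-2 | late MCI | **none** | none |

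At MoCA 26, a drop in recall from 9 to 8, 5 to 4 or 3 to 2 takes the participant from early MCI to no group. The healthy and SCI groups are closed to that person, because they need CDR 0 and higher recall. Mild AD is closed because it needs CDR 1.0 and MoCA of at most 24. At 25 and at 27 the two strata are treated alike, so the unequal treatment is confined to a score of exactly 26.

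**2. Size, under an assumption.** The protocol gives no MoCA distribution. Assume that, among people who otherwise meet either set of MCI criteria, MoCA is normal with mean μ = 23 or 24 and SD 2.5, rounded to whole points.

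*Share scoring exactly 26:* Φ((26.5 − μ)/2.5) − Φ((25.5 − μ)/2.5).
- μ = 23: Φ(1.4) − Φ(1.0) = 0.9192 − 0.8413 = 0.078
- μ = 24: Φ(1.0) − Φ(0.6) = 0.8413 − 0.7257 = 0.116

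*Share scoring 20-25:* Φ((25.5 − μ)/2.5) − Φ((19.5 − μ)/2.5).
- μ = 23: Φ(1.0) − Φ(−1.4) = 0.761
- μ = 24: Φ(0.6) − Φ(−1.8) = 0.690

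*Gap in mean MoCA from truncation alone:* with the same distribution in both strata, the gap between limits 20-26 and 20-25 is [P(26)/P(20-26)] × (26 − mean within 20-25).
- μ = 23: 0.0779/0.8385 × (26 − 22.69) = 0.31 points
- μ = 24: 0.1156/0.8054 × (26 − 23.07) = 0.42 points

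*People turned away:* this needs the late-MCI share of the 100, which is not stated. If it were half, filling 50 late-MCI places would turn away 50 × 0.078/0.761 = 5.1 to 50 × 0.116/0.690 = 8.4 people.

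**The case against.** **The ceilings may be graded on purpose.** They fall by one point per stage: 26 for early MCI, 25 for late MCI, 24 for mild AD. The text does not show whether this is design or slip. That stands, and it is why justifying the difference is an acceptable answer. A deliberate gradient would still leave the hole at 26 and truncate the two strata unequally.

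**Strict criteria leave many profiles unplaced.** This is true: for example, CDR 0 with MoCA 25 fits no group, nor does CDR 0.5 with recall 12 at 16 or more years of education. What sets this cell apart is that worse recall, with all else equal, removes eligibility at 26 but not at 25.

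**The effect is small.** This stands too. Those affected are screen failures in a plan that screens about 650 to enrol 350, and a gap of 0.3-0.4 points is little on a 30-point scale. The protocol pools early and late MCI in its target and names no early-versus-late comparison in its objectives.

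**Stronger readings that the protocol does not support.** A reader might infer that 26 also causes a conflict between early MCI and the healthy or SCI groups, since it counts as normal in one place and impaired in another. It does not: CDR 0 against 0.5 separates them, early MCI also needs the NIA-AA criteria (3.6.5), and no profile fits two groups. Nor does the share scoring 26 or more (16-27% under the same assumption) measure the problem, because both MCI strata refuse 27 and above.

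**Conclusion.** Sections 3.6.3 and 3.7.3 are inconsistent, and nothing else in the protocol resolves it. That part rests on the text alone: at MoCA 26 with CDR 0.5, the stratum for the more impaired recall is closed while the stratum for the better recall is open.

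The size rests on the assumed distribution. It is about 8-12% of otherwise late-MCI candidates and a built-in difference of about 0.3-0.4 MoCA points. The number of people cannot be fixed without the late-MCI share; the 5 to 8 above holds only if that share is half.

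The point does not affect a stated sample size and does not place anyone in two groups. It bears on who enters the MCI group, on its early-late split and on any contrast between the two strata. Severity is minor to moderate.

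**What to change.** Reconcile 3.6.3 and 3.7.3 so that both MCI strata have the same MoCA upper limit, or state why the limits differ. The protocol does not show which limit is intended, so that choice is for the sponsor.

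Keep participants already enrolled in their assigned group. Moving them is not an option under the current criteria: CDR 0.5 bars an early-MCI participant with MoCA 26 from the healthy and SCI groups, and the score bars late MCI and mild AD. Flag early-MCI participants with MoCA 26, and repeat any early-versus-late or MCI-group comparison without them as a sensitivity analysis.

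The cost is a short amendment to the eligibility text and one further run on data already held. If the common limit were set at 25, the flagged participants would no longer meet any group's criteria, so the amendment should say that their existing assignment stands.

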3.7.3 Has a score of 20 to 25 (inclusively) on the MoCA

3.7.4 Has a CDR (Clinical Dementia Rating) score of 0.5

3.7.5 Meets NIA-AA clinical criteria for MCI-AD

3.8 INCLUSION CRITERIA FOR MILD AD (ALZHEIMER’S DISEASE) PATIENTS

3.8.1 Has a deferred recall score for the logical story (Wechsler Memory Scale, max score of 25)

- I. ≤ 8 for 16 years of education and more
- II. ≤ 4 for 8-15 years of education
- III. ≤ 2 for 0-7 years of education.

3.8.2 Has a score of 13 to 24 (inclusively) on the MoCA

3.8.3 Has a CDR (Clinical Dementia Rating) score of 1.0

3.8.4 Meets NIA-AA clinical criteria for probable Alzheimer's.

3.9 INCLUSION CRITERIA FOR ALL ELDERLY PARTICIPANT GROUPS

- Be 65 years of age and older
- Live in the community or an independent living residence (or an equivalent living environment)
- T-MMSE score of 17 or more ($\geq 17/26$) (7)
- Understand, read and write in French or English
- Possess sufficient vision and hearing to complete the neuropsychological tests
- For participants with mild Alzheimer's disease (AD), they must be accompanied during clinical visits. For other participants, they must have a close relation who can answer some questions (in person, by phone, or in writing).
- Consent to respond to questionnaires on health status; undergo a physical examination and complete a neuropsychological assessment; take a blood test.

3.10 EXCLUSION CRITERIA FOR ALL ELDERLY PARTICIPANT GROUPS

- Plan on moving from Quebec province within the next three years
- Score of 20 or more ($\geq 20/27$) on the PHQ-9 (8)
- CDR score greater than 1 (>1)
- Have a disease affecting or an impairment to the central nervous system:
 - I. A subdural hematoma (active or past)
 - II. A subarachnoid haemorrhage (active or past)
 - III. A primary or metastatic cerebral cancer
 - IV. Epilepsy (active)
 - V. Dementia other than mild Alzheimer's or another neurodegenerative disease
- Have undergone intracranial surgery
- Alcohol, drug or narcotic dependency
- Regularly consume benzodiazepines, at an equivalence of 1 mg per day of lorazepam taken orally
- Have a disease/condition that, in the opinion of the specialist, is related to cognitive deficits and could disrupt the subject's participation in the project.

NOTE: All assessment visits must be planned to take place more than 2 months after a hospitalization lasting more than or as long as 72 hours (≥ 72 hours) or more than 2 months after having undergone general anaesthesia.

3.11 POSSIBLE EXCLUSION CRITERIA FOR MORE SPECIFIC INTERVENTIONS

3.11.1 For magnetic resonance imaging (MRI / MRS)

- Pregnancy
- Pacemaker
- Defibrillator (an apparatus for cardiac rhythm)
- A prosthetic heart valve (heart prosthesis)
- A Swan-Ganz catheter (a tube in the pulmonary artery on the thorax)
- A subdural insulin or metallic chemotherapy pump
- A neurostimulator, a cerebral neurostimulator, a clip on a cerebral aneurysm (a clip on a blood vessel within the brain)
- A metallic prosthesis or rod (following surgery)
- A metallic strapping (metal support on a bone)
- A cochlear and ocular implant (an implant in an ear or an eye)
- A penial implant
- An intraocular metallic fragment (metallic debris in the eye)
- A patch on the skin for administering a medication

Other situations that could cause an **impediment to or cessation of the MRI exam**

- The presence of piercings, tattoos, permanent makeup
- Dental braces
- Acute claustrophobia (unpleasant sensation when in closed spaces).

3.11.2 Lumbar puncture

- Take anticoagulants such as warfarin, Dabigatran or heparin.
- Allergy/hypersensitivity to local anaesthetics

3.11.3 PET

- Women who are not sterile (surgically or more than 2 years postmenopause)
- Women who are breastfeeding.

3.12 INCLUSION / EXCLUSION CRITERIA FOR THE YOUNG PARTICIPANTS

3.12.1 Inclusion criteria for the young participants

- Men or women between the ages of 20 and 45
- Living in the community
- Have consented to the collection of cerebrospinal fluid by LP

3.12.2 Exclusion criteria for the young participants

- In the past 2 months, have been hospitalized for a period greater or equal to 72 hours (≥ 72 hours) or have undergone general anaesthesia.
- Have a disease affecting or an impairment to the central nervous system:
 - I.* Subdural hematoma
 - II.* Subarachnoid haemorrhage
 - III.* Cerebral tumour or metastasis

- IV.** Infectious or inflammatory cerebral disease
- V.** Epilepsy
- VI.** Neurodegenerative disease
- VII.** Dementia

- Have parents or grandparents who had or have neurodegenerative diseases.
- Presence of antecedents of repeated minor traumatic brain injuries or people who participate or participated in contact sports (ex. hockey, football, soccer) where brain injuries were likely
- Have undergone intracranial surgery
- Have a chronic psychiatric disease
- Be treated for depression
- Have a disease/condition requiring medication, or have undergone or are undergoing radiotherapy or chemotherapy
- Have had an alcohol or any other drug dependency at some point over the last 2 years
- Use narcotics or benzodiazepines on a regular basis
- For women, pregnancy

3.13 PARTICIPANT WITHDRAWAL

For any participant who decides to withdraw from the project, a short telephone follow-up will be conducted. If the participant does not object, a few questions will be asked regarding the reason for withdrawing from the project.

